***All treatments and assessments will be administered OU.***

#### **7.2.2. Visit 2 (Treatment 2) – Day 4**

Visit 2 may occur 3 to 5 days after Visit 1. On the morning of Visit 2, subjects will undergo certain assessments immediately *prior* to receiving Treatment 2 at 0 minutes:

- Urine pregnancy test for females of childbearing potential
- HR/BP
- Concomitant medications
- [REDACTED]
- [REDACTED]  
[REDACTED]

Treatment 2 (LDP or No Treatment) is unmasked and will be administered on Visit 2 by a designated, unmasked, Site Staff member, distinct from the Site Staff member recording measurements/assessments.

After instillation of Treatment 2 (LDP or No Treatment), subjects will undergo certain assessments at multiple timepoints after Time 0 (from 30 minutes to 6 hours):

- PD

- DCNVA (mesopic and photopic), BCDVA (mesopic and photopic), BCIVA (photopic) – monocular and binocular
- Conjunctival hyperemia
- Adverse events (AEs)
- Subjective ocular tolerability

Biomicroscopy, IOP, and ophthalmoscopy will be performed at the 6-hour timepoint.

There is a window of [REDACTED] for every timepoint to complete measurement of the primary endpoint of photopic DCNVA. Sites should start pupil diameter measurements approximately 5 minutes prior to each timepoint in order to allow sufficient time to perform the primary endpoint of photopic DCNVA at the target timepoint.

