- Percentage of subjects with improvement or loss in **BCDVA** (mesopic) from Baseline (Visit 1) to Visit 2 at 1 hour, 3 hours, and 6 hours of ≥ 5 , ≥ 10 , and ≥ 15 letters comparing Nyxol + LDP to Nyxol alone, Placebo + LDP, and Placebo alone
- Change in **BCDVA** (mesopic) from Baseline (Visit 1) to Visit 2 at 1 hour, 3 hours, and 6 hours of ≥ 5 , ≥ 10 , and ≥ 15 letters comparing Nyxol + LDP to Nyxol alone, Placebo + LDP, and Placebo alone
- Change and percent change in **Pupil Diameter (PD)** (mesopic and photopic) from Baseline (Visit 1) to Visit 2 at 30 minutes, 1 hour, 2 hours, 3 hours, 4 hours, and 6 hours comparing Nyxol + LDP to Nyxol alone, Placebo + LDP, and Placebo alone
- Percentage of subjects with a **PD** (mesopic and photopic) of < 2.4 , < 2.2 , < 2.0 , < 1.8 , < 1.6 , and < 1.4 mm measured on Visit 2 at 30 minutes, 1 hour, 2 hours, 3 hours, 4 hours, and 6 hours comparing Nyxol + LDP to Nyxol alone, Placebo + LDP, and Placebo alone
- Percentage of subjects with a **PD** (mesopic and photopic) of 1.6 to < 2 mm, 2 to < 2.4 mm, and 1.2 to < 1.6 mm measured at 30 minutes, 1 hour, 2 hours, 3 hours, 4 hours, and 6 hours comparing Nyxol + LDP to Nyxol alone, Placebo + LDP, and Placebo alone
- Percentage of subjects with a ≥ 3 -line improvement in photopic binocular **DCNVA** with a **PD** (photopic and mesopic) of 1.6 to < 2 mm at 30 minutes, 1 hour, 2 hours, 3 hours, 4 hours, and 6 hours comparing Nyxol + LDP to Nyxol alone, Placebo + LDP, and Placebo alone
- Percentage of subjects with Baseline **DCNVA** (photopic and mesopic) $\leq 20/63$, $\leq 20/80$, $\leq 20/100$, $\leq 20/125$, and $\leq 20/160$ with a ≥ 15 -letter improvement in **DCNVA** on Visit 2 at 30 minutes, 1 hour, 2 hours, 3 hours, 4 hours, and 6 hours comparing Nyxol + LDP to Nyxol alone, Placebo + LDP, and Placebo alone
- Percentage of subjects with Baseline **DCNVA** (photopic and mesopic) from 25/50 to 20/63, 20/80 to 20/100, and 20/125 to 20/160 with a ≥ 15 -letter improvement in **DCNVA** on Visit 2 at 30 minutes, 1 hour, 2 hours, 3 hours, 4 hours, and 6 hours comparing Nyxol + LDP to Nyxol alone, Placebo + LDP, and Placebo alone
- Percentage of subjects with improvement of ≥ 5 , ≥ 10 , and ≥ 15 letters in **DCNVA** (photopic) from Baseline (Visit 1) to Visit 2 at 0 minutes, comparing Nyxol to Placebo treated subjects
- Change in **DCNVA** (photopic) from Baseline (Visit 1) to Visit 2 at 0 minutes, comparing Nyxol to Placebo treated subjects

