6. SAMPLE SIZE

A sample size of approximately 140 subjects (40 for Nyxol + LDP and Placebo alone arms and 30 for each of the other 2 arms) who are evaluable for efficacy is needed for the study. The primary treatment comparison will be Nyxol + LDP compared to Placebo alone.

Subjects will be randomized 4:3:3:4 to Nyxol + LDP, Nyxol + No Treatment 2 (Nyxol alone), Placebo + LDP, and Placebo + No Treatment 2 (Placebo alone), respectively.

It is assumed that there will be approximately 7% drop-out between Visit 1 and end of Visit 2. To account for this drop-out, a total of approximately 152 subjects will be randomized into the study.

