7.4. Planned Study Analyses

7.4.1. Statistical Summaries: Descriptive and Inferential

Categories for data presentation and analysis will consist of each treatment group: Nyxol + LDP, Nyxol + No Treatment 2 (Nyxol alone), Placebo + LDP, Placebo + No Treatment 2 (Placebo alone).

All statistical tests will be two-sided and a difference resulting in a p-value of less than or equal to 0.05 will be considered statistically significant. The p-values for the analysis of secondary efficacy endpoints and safety endpoints will be considered descriptive. All p-values will be rounded to and displayed in four decimals. If a p-value less than 0.0001 occurs, it will be shown in tables as <0.0001.

Descriptive summaries of variables will be provided where appropriate. For continuous variables, the number of non-missing values (n), mean, standard deviation, median, minimum, and maximum will be tabulated by treatment group. For categorical variables, the counts and proportions of each value will be tabulated by treatment group. Expansion of descriptive table categories within each treatment may occur if such elaborations are thought to be useful.

All study-related data collected will be presented in listings. Study-related data not subject to analysis according to this plan will not appear in any tables or graphs but will be included in the data listings.

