9.1.2. Secondary Efficacy Analyses

Secondary efficacy endpoints are indicated in Section 4.2.2. Secondary efficacy endpoints will be analyzed by study eye, fellow eye, and binocular (if available) using the PP population, and the mITT population for selected endpoints (see the list of planned tables, Section 12.1, for details).

All continuous secondary endpoints derived from VA assessments, such as change in DCNVA, DCIVA, and BCDVA, will be analyzed using Early Treatment Diabetic Retinopathy Study (ETDRS) letters correctly read. Any secondary endpoints using Snellen measurements will be converted from letters read as follows:

Table 2 Snellen Equivalents to VA Assessment Letters Read

DCNVA/DCIVA letters	Snellen	BCDVA letters
≥75	20/15	≥60
70 - 74	20/20	55 - 59
65 - 69	20/25	50 - 54
60 - 64	20/32	45 - 49
55 - 59	20/40	40 - 44
50 - 54	20/50	35 - 39
45 - 49	20/63	30 - 34
40 - 44	20/80	25 - 29
35 - 39	20/100	20 - 24
30 - 34	20/125	15 - 19
25 - 29	20/160	10 - 14
<25	20/200	<10

Each of the continuous secondary efficacy endpoints will be analyzed using analysis of covariance (ANCOVA), with observed value as the dependent variable, treatment, and light/dark irides as factors, and the respective baseline value included as the covariate. Another ANCOVA will be applied with change from baseline as the dependent variable using the same factors and covariates.

The output from each ANCOVA will include the LSM and SE for all treatment groups, along with each LSM, the 95% CI and associated p-value for Nyxol + LDP vs. Nyxol alone, Placebo + LDP, and Placebo alone. Continuous pupil diameter endpoints will be assessed using the study eye, fellow eye, and best eye, which is defined as the eye with the greatest reduction in diameter.

For each of the secondary endpoints related to percent of subjects achieving certain criteria, the analysis will be performed using a logistic regression model with treatment and light/dark irides as factors, and the respective baseline as a covariate. For each analysis, the percentage of subjects in each treatment group meeting the criteria will be presented, and the OR with 95% CI and p-value will be provided for Nyxol + LDP vs. Nyxol alone, Placebo + LDP, and Placebo alone. Categorical pupil diameter endpoints will be assessed using the study eye, fellow eye, and either eye, which is defined as achieving a given criterion in either eye.

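### The 0-minute near-vision endpoints are defined as Nyxol versus Placebo in SAP 4.2.2, but the general rules in SAP 7.4.1 and 9.1.2 prescribe only four-arm, Nyxol + LDP contrasts and make no exception

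*SAP*

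**What the plan says.** SAP 4.2.2 lists two endpoints at Visit 2, 0 minutes: the percentage of subjects gaining at least 5, 10 and 15 letters of photopic DCNVA, and the change in photopic DCNVA. Both are measured "from Baseline (Visit 1) to Visit 2 at 0 minutes, comparing Nyxol to Placebo treated subjects". The other between-arm endpoints in that section name Nyxol + LDP against three arms, so the different wording looks deliberate.

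Protocol 7.2.2 places the first Visit 2 assessments just prior "to receiving Treatment 2 at 0 minutes". At that moment no subject has had LDP.

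The analysis sections do not carry the two-group comparison through:

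- SAP 7.4.1: "Categories for data presentation and analysis will consist of each treatment group: Nyxol + LDP, Nyxol + No Treatment 2 (Nyxol alone"), followed by the other two arms. No pooled Treatment 1 category is given.
- SAP 9.1.2, continuous endpoints: the ANCOVA rule covers each secondary endpoint of this type, and the contrasts are the estimate, interval and "associated p-value for Nyxol + LDP vs. Nyxol alone, Placebo + LDP, and Placebo alone".
- SAP 9.1.2, percentage endpoints: "the OR with 95% CI and p-value will be provided for Nyxol + LDP vs. Nyxol alone, Placebo + LDP, and Placebo alone".

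Protocol 9.3.5 calls for placebo-corrected least-squares means for each treatment difference, but it does not pool the arms by Treatment 1 either.

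**The concern.** The endpoint definition and the analysis rule ask for different things. At 0 minutes, Nyxol + LDP and Nyxol alone are the same treatment, and so are Placebo + LDP and Placebo alone. A programmer who applies 9.1.2 literally would produce three contrasts:

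- Nyxol + LDP v Nyxol alone. The two groups have had identical treatment, so any difference is chance.
- Nyxol + LDP v Placebo alone. This is a Nyxol v Placebo comparison on part of the sample.
- Nyxol + LDP v Placebo + LDP. This is a second partial Nyxol v Placebo comparison.

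The single comparison that 4.2.2 names would not appear. One question would get two estimates and two p-values, with no rule for which is the result. What is at stake is a clear and precise randomised estimate of the effect of evening Nyxol on near vision the next morning.

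**Working it through.** **Inputs.** Planned evaluable numbers from SAP 6: "40 for Nyxol + LDP and Placebo alone arms and 30 for each of the other 2 arms". Allocation 4:3:3:4 and drop-out of about 7% come from the same section.

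**The plan's own figures.** 140 × 4/14 = 40 and 140 × 3/14 = 30, so the arms are 40/30/30/40 as stated. Inflating for drop-out, 140 / (1 − 0.07) = 150.5, or 151, which agrees with the stated approximate 152.

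**Groups at 0 minutes.** Nyxol: 40 + 30 = 70. Placebo: 30 + 40 = 70.

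**Standard error of a difference in means, in SD units:** √(1/n₁ + 1/n₂), assuming a common SD and ignoring covariate adjustment.

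| Contrast | n | SE factor | Relative to pooled |
|---|---|---|---|
| Pooled Nyxol v pooled Placebo (4.2.2) | 70 v 70 | √(2/70) = 0.169 | 1 |
| Nyxol + LDP v Placebo alone (9.1.2) | 40 v 40 | √(2/40) = 0.224 | 1.32 |
| Nyxol + LDP v Placebo + LDP (9.1.2) | 40 v 30 | √(1/40 + 1/30) = 0.242 | 1.43 |
| Nyxol + LDP v Nyxol alone (9.1.2) | 40 v 30 | not a Nyxol v Placebo contrast | – |

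For a crude log odds ratio, the 1.32 carries over, because both groups shrink by the same factor. The 1.43 then depends on the two response rates and lies between √(70/40) = 1.32 and √(70/30) = 1.53.

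**Who is used.** The two partial contrasts together involve 40 + 40 + 30 = 110 of 140 subjects. The 30 in the Nyxol-alone arm (30/140 = 21%) enter neither. Even if the two were combined, the comparison would be 40 v 70, with SE factor √(1/40 + 1/70) = 0.198, which is 17% above 0.169.

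**Detectable difference.** At two-sided 5% and 80% power, (1.96 + 0.84) × √(2/n) gives 0.63 SD for 40 v 40 and 0.47 SD for 70 v 70.

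**Power, for illustration only.** The documents give no 0-minute effect size. For assumed mean differences of 0.4, 0.5 and 0.6 SD, power is 43%, 61% and 77% with 40 v 40, against 66%, 84% and 94% with 70 v 70. Protocol 2.2 reports 63.2% v 20.0% gaining at least one line in an earlier 14-day trial. At those rates power is 98.5% for 40 v 40, 97% for 40 v 30 and about 100% for 70 v 70.

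**The case against.** The strongest reply is that the plan already names the right comparison. SAP 4.2.2 is as much a part of it as 9.1.2, 9.1.2 refers back to 4.2.2 for its endpoints, and a specific definition would normally override general output wording. A careful programmer would probably pool by Treatment 1. This stands as a reason for optimism. It does not remove the conflict, because 9.1.2 speaks of each endpoint and 7.4.1 admits only four categories.

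Second, the list of planned tables (SAP 12.1) and the example code are redacted, so a pooled table may exist. That stands. If it does exist, the text of 9.1.2 still disagrees with it.

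Third, the ANCOVA output includes least-squares means for all four arms, so a pooled mean difference could be approximated from planned output. That is partly right, but it yields no prespecified interval, and no adjusted odds ratio for the responder endpoints.

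Fourth, secondary p-values are descriptive, and no stated efficacy objective concerns Nyxol v Placebo. Both statements are correct, and they limit the importance of the point.

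A reader might infer that the trial is committed to a 40 v 40 comparison and throws away 60/140 = 43% of its subjects. The documents do not support this. The 43% describes one contrast only, 110 of 140 subjects enter some Nyxol v Placebo contrast, and 4.2.2 points to the full comparison. Nor do they support a firm claim of lost power: the effect sizes for which power differs are assumptions, and at the one documented pair of rates every contrast has at least 97%.

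**Conclusion.** The inconsistency is real and should be resolved, but its reach is modest. Applied literally to the 0-minute endpoints, 9.1.2 gives one uninformative contrast and two partial ones, with standard errors about 32% and 43% larger than the comparison defined in 4.2.2. It also leaves the 30 Nyxol-alone subjects out of any Nyxol v Placebo contrast. The consequence is confined to the precision and clarity of two secondary, descriptive endpoints. The primary analysis is not affected.

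The figures rest on the planned evaluable numbers and a common SD; actual counts will be those of the PP population, or mITT where selected. The 70 v 70 is derived, since 4.2.2 does not use the word pooled, but before Treatment 2 its wording has no other natural reading. The conclusion also rests on the readable text alone.

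**What to change.** In SAP 9.1.2, state that the 0-minute DCNVA endpoints are analysed as defined in 4.2.2. Use a two-level Treatment 1 factor (Nyxol + LDP and Nyxol alone pooled, against Placebo + LDP and Placebo alone pooled), with irides type and baseline DCNVA in the model. Report one contrast, in place of the Nyxol + LDP contrasts at that time point. Add a matching exception to the four-arm categories in SAP 7.4.1, and check that the planned tables agree.

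The cost is two sentences and, if not already planned, a two-column table shell. No new data are needed. Both treatments are randomised at Visit 1, so pooling by Treatment 1 keeps the comparison randomised. Making the change before unmasking avoids a later choice among contrasts.

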**Table 1: Efficacy of 1% Nyxol in Reducing Pupil Diameter in Mesopic Conditions in Phase 2 Trials**

Study	Group	Mesopic Conditions				
		Pre-Treatment (Baseline) Pupil Diameter	Post-Treatment Pupil Diameter	Change (%)	p-value compared to baseline	p-value compared to placebo
NYX-SNV (1)	Placebo (N = 16)	6.6 mm	6.4 mm	-0.2 mm (-3%)	p = 0.08	p < 0.0001
	1.0% Nyxol (N = 32)	6.5 mm	5.2 mm	-1.3 mm (-20%)	p < 0.0001	
NYX-01a2 (2)	Placebo (N = 38)	6.25 mm	6.31 mm	0.07 mm (+1%)	p = 0.6	p < 0.0001
	1.0% Nyxol (N = 40)	6.17 mm	5.31 mm	-0.86 mm (-14%)	p < 0.0001	
NYXG-201 (3)	Placebo (N = 20)	4.57 mm	4.52 mm	-0.05 mm (-1%)	p = 0.6178	p < 0.0001
	1.0% Nyxol (N = 19)	4.69 mm	3.70 mm	-1.00 mm (-21%)	p < 0.0001	

Nyxol was observed to be well tolerated at single doses up to and including 1.0% daily in each eye. This includes 59 subjects who received multiple doses of up to 1% Nyxol for at least 14 days. Safety of the subjects in these trials was evaluated by adverse event (AE) monitoring, physical examinations, and vital sign assessments. Across all trials, no healthy volunteers or subjects reported a treatment-emergent serious adverse event (SAE). No deaths occurred in any of the trials. No clinically meaningful changes were observed in physical examinations or vital signs, including blood pressure (BP) and heart rate (HR). AEs reported were mild to moderate in intensity with the most common being transient conjunctival hyperemia and ocular irritation; however, Nyxol dosing at or near bedtime was observed to mitigate or minimize these side effects during the daytime.

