### **5. SUBJECT INCLUSION AND EXCLUSION CRITERIA**

#### **5.1 Subject Inclusion Criteria**

1. Males or females  $\geq$  40 and  $\leq$  64 years of age.
2. Able to comply with all protocol-mandated procedures independently and to attend all scheduled office visits.
3. Able and willing to give signed informed consent.
4. Able to self-administer study medication throughout the study period.
5. BCDVA of 0.0 LogMAR (20/20 Snellen equivalent) or better in each eye under photopic conditions.
6. DCNVA of 0.4 LogMAR (20/50 Snellen equivalent) or worse under photopic conditions in each eye and binocularly.
7. Subjects who depend on reading glasses or bifocals in which their binocular best-corrected near VA is 0.1 LogMAR (20/25 Snellen equivalent) or better.

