4.1. Study Objectives

The objectives of this study are as follows:

Primary objective

- To evaluate the efficacy of Nyxol + LDP to improve distance-corrected near visual acuity (DCNVA) compared to Placebo alone in subjects with presbyopia

Secondary objectives

- To evaluate the efficacy of Nyxol + LDP to prevent >1 line of loss of best-corrected distance visual acuity (BCDVA)
- To evaluate the efficacy of Nyxol + LDP to improve DCNVA compared to Nyxol alone or LDP alone
- To evaluate the ability of Nyxol + LDP to produce the “pinhole” pupil size (approximately 1.6-2 mm)
- To evaluate the efficacy of Nyxol + LDP to improve distance-corrected intermediate visual acuity (DCIVA) and BCDVA
- To evaluate the effect of iris color on the efficacy of Nyxol + LDP
- To evaluate the ocular and systemic safety of Nyxol + LDP and each component individually

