4.2.2. Secondary Endpoints

Secondary endpoints for efficacy and safety assessments include the following:

Efficacy:

Secondary efficacy endpoints will be analyzed by study eye, fellow eye, and binocular unless otherwise indicated, and will include:

- Percentage of subjects with improvement of ≥ 15 letters in **DCNVA** (photopic) at 1 hour and with < 5 letters of loss in photopic binocular **BCDVA** from Baseline (Visit 1) to Visit 2 at 30 minutes, 1 hour, 2 hours, 3 hours, 4 hours, and 6 hours comparing Nyxol + LDP to Nyxol alone, Placebo + LDP, and Placebo alone
- Percentage of subjects with improvement of ≥ 5 , ≥ 10 , and ≥ 15 letters in **DCNVA** (photopic) from Baseline (Visit 1) to Visit 2 at 30 minutes, 1 hour, 2 hours, 3 hours, 4 hours, and 6 hours comparing Nyxol + LDP to Nyxol alone, Placebo + LDP, and Placebo alone
- Change in **DCNVA** (photopic) from Baseline (Visit 1) to Visit 2 at 30 minutes, 1 hour, 2 hours, 3 hours, 4 hours, and 6 hours comparing Nyxol + LDP to Nyxol alone, Placebo + LDP, and Placebo alone
- Percentage of subjects with improvement in **DCNVA** (mesopic) from Baseline (Visit 1) to Visit 2 at 2 hours, 4 hours, and 6 hours of ≥ 5 , ≥ 10 , and ≥ 15 letters comparing Nyxol + LDP to Nyxol alone, Placebo + LDP, and Placebo alone
- Change in **DCNVA** (mesopic) from Baseline (Visit 1) to Visit 2 at 2 hours, 4 hours, and 6 hours of ≥ 5 , ≥ 10 , and ≥ 15 letters comparing Nyxol + LDP to Nyxol alone, Placebo + LDP, and Placebo alone
- Percentage of subjects with improvement in **DCIVA** (photopic) from Baseline (Visit 1) to Visit 2 at 1 hour, 3 hours, and 6 hours of ≥ 5 , ≥ 10 , and ≥ 15 letters comparing Nyxol + LDP to Nyxol alone, Placebo + LDP, and Placebo alone
- Change in **DCIVA** (photopic) from Baseline (Visit 1) to Visit 2 at 1 hour, 3 hours, and 6 hours comparing Nyxol + LDP to Nyxol alone, Placebo + LDP, and Placebo alone
- Percentage of subjects with improvement or loss in **BCDVA** (photopic) from Baseline (Visit 1) to Visit 2 at 30 minutes, 1 hour, 2 hours, 3 hours, 4 hours, and 6 hours of ≥ 5 , ≥ 10 , and ≥ 15 letters comparing Nyxol + LDP to Nyxol alone, Placebo + LDP, and Placebo alone

- Change in **BCDVA** (photopic) from Baseline (Visit 1) to Visit 2 at 30 minutes, 1 hour, 2 hours, 3 hours, 4 hours, and 6 hours comparing Nyxol + LDP to Nyxol alone, Placebo + LDP, and Placebo alone

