10.8. Other Safety Measures

The efficacy endpoint "Percentage of subjects with improvement or loss in **BCDVA** (photopic) from Baseline (Visit 1) to Visit 2 at 30 minutes, 1 hour, 2 hours, 3 hours, 4 hours, and 6 hours of ≥ 5 , ≥ 10 , and ≥ 15 letters comparing Nyxol + LDP to Nyxol alone, Placebo + LDP, and Placebo" will be analyzed using the Safety Population for photopic BCDVA.

Urine pregnancy tests for females of childbearing potential will be presented in by-subject listings. Dry eye tests (tear break-up time and cornea fluorescein staining), performed only at baseline, will also be listed.

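### SAP 9.1.2 requires a logistic-regression OR, CI and p-value for each secondary responder endpoint, but its visible text has no rule for a compared arm with no, or only, responders

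*SAP*

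**What the plan says.** SAP 9.1.2 analyses each percent-of-subjects endpoint by logistic regression, with treatment and irides as factors and the matching baseline as covariate. It commits to three comparisons: "the OR with 95% CI and p-value will be provided for Nyxol + LDP vs. Nyxol alone, Placebo + LDP, and Placebo alone". It then repeats the analysis within each iris colour, without the irides factor. SAP 7.4.1 treats secondary p-values as descriptive.

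Two groups of endpoints in SAP 4.2.2 matter here.

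- **Pupil diameter.** Mesopic and photopic cut-offs "of < 2.4 , < 2.2 , < 2.0 , < 1.8 , < 1.6 , and < 1.4 mm" at six timepoints. They serve a stated objective in SAP 4.1, "To evaluate the ability of Nyxol + LDP to produce the" pinhole pupil. Protocol Table 1 ("Table 1: Efficacy of 1% Nyxol in Reducing Pupil Diameter in Mesopic Conditions in Phase 2 Trials") gives post-treatment placebo means of 6.4, 6.31 and 4.52 mm.
- **Photopic BCDVA.** "Percentage of subjects with improvement or loss in" BCDVA, at 5, 10 and 15 letters. Entry requires "BCDVA of 0.0 LogMAR (20/20 Snellen equivalent) or better in each eye under photopic conditions" (Protocol 5.1). SAP 10.8 adds that this endpoint "will be analyzed using the Safety Population for photopic BCDVA".

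No visible text in either document names exact or penalised logistic regression, a minimum event count or a counts-only fallback. Fisher's exact test appears only for the pooled tolerability categories in SAP 10.4.

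**The concern.** If one compared arm has no responders, the likelihood for the treatment log-OR keeps rising without limit. Ordinary software then either warns and stops or prints a very large OR with a very large standard error. A Wald test on that output gives a p-value near 1, so the table looks weakest where the arms differ most.

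At stake are the ORs, CIs and p-values for such endpoints, including some that serve the pinhole objective. If nothing is written beforehand, the method for those cells will be chosen after the empty cells have been seen.

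**Working it through.** **Arm sizes (SAP 6).** 140 evaluable at 4:3:3:4 gives 140 × 4/14 = 40 and 140 × 3/14 = 30, as the plan states. With stratification 1:1 by iris colour this is about 20 or 15 per arm per stratum. The protocol's power statement uses 38 per arm; its assumed rates are redacted.

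**1. Mesopic pupil, Placebo alone.** The means come from Protocol Table 1. No SD is given, so 0.8 to 1.2 mm is assumed, with a normal distribution. P(0 of n) = [1 − Φ((cut-off − mean)/SD)]^n, with n = 40.

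Worked case, mean 4.52 mm, <2.0 mm:
- SD 0.8: z = −3.15, tail 0.0008, 0.9992^40 = 97%.
- SD 1.2: z = −2.10, tail 0.0179, 0.9821^40 = 49%.

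| Cut-off (mm) | P(0 of 40) at 4.52 mm, SD 0.8 to 1.2 |
|---|---|
| <1.4 | 99.8% to 83% |
| <1.6 | 99% to 74% |
| <1.8 | 99% to 62% |
| <2.0 | 97% to 49% |
| <2.2 | 93% to 34% |
| <2.4 | 85% to 21% |

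At means of 6.31 and 6.4 mm the probability is about 98% or more at every cut-off. SAP 9.1.2 also uses an either-eye definition. Treating eyes as independent (exponent 80, a lower bound), <2.0 mm at 4.52 mm gives 94% to 24%.

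**2. Would the combination arm have responders?** Protocol 2.3 expects a 20% reduction from Nyxol and a further 20% from LDP.
- From the baseline of 4.69 mm in the Nyxol arm of the glaucoma and presbyopia trial: 4.69 × 0.8 × 0.8 = 3.00 mm. Below 2.0 mm: Φ(−1.25) = 10.6% at SD 0.8 and Φ(−0.83) = 20% at SD 1.2, or about 4 to 8 of 40. One empty arm against a non-empty one is a realistic pattern.
- From 6.5 mm: 6.5 × 0.64 = 4.16 mm. Both arms may then be empty at the small cut-offs.

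**3. Iris strata.** At an assumed arm rate of 5%, P(no responders) is 0.95^20 = 36% and 0.95^15 = 46%.

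**4. What the model returns.** The counts are illustrative. The fits are treatment-only unless stated.

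| Result | Wald p | Fisher p | Firth penalised LR p |
|---|---|---|---|
| 12/38 vs 0/38 | >0.99 | 0.0002 | 0.00006 |
| 6/20 vs 0/20 | >0.99 | 0.020 | 0.008 |

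For 12/38 vs 0/38 the Firth OR is (12.5/26.5)/(0.5/38.5) = 36, with profile CI 4.4 to 4,728. One placebo responder removes the problem. For 12/38 vs 1/38, OR = (12/26)/(1/37) = 17.1, SE = √(1/12 + 1/26 + 1 + 1/37) = 1.07, z = 2.65 and Wald p = 0.008.

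In a fit with all four arms, irides and baseline, with 12/40 vs 0/40, the log-OR drifted from 8.3 to 15.3 to 28.5 as iterations increased. The SE went from 16 to 520 to about 377,000, and the Wald p from 0.60 to about 1.

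**5. Photopic BCDVA gain of at least 15 letters.** SAP 9.1.2 converts letters by its Table 2 ("Any secondary endpoints using Snellen measurements will be converted from letters read as follows"), where 20/20 starts at 55 letters. A responder needs at least 55 + 15 = 70 letters, 10 above the start of the best band at 60. In LogMAR this is 0.0 − 0.30 = −0.30, about 20/10. At an assumed event rate of 0.1% to 0.5%, P(no event in two arms of 40) = (1 − p)^80 = 92% to 67%. No events in any arm is the expected result, and no OR is then estimable by any method.

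**The case against.** **Redaction.** SAP 9.1.2 says only that a logistic regression model is used. It does not say maximum likelihood or Wald, and the redacted example code or table list could contain a Firth or exact option. This stands. The point is therefore limited to the visible text, and the p-value near 1 is conditional on a Wald test.

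**Assumed SDs and other populations.** The means above 6 mm come from trials in night-vision or dim-light disturbance, one with a median age of 39. Only the 4.52 mm trial is described as presbyopic. There the probability falls to 21% at the widest cut-off and largest SD. This stands as a limit on the size: an empty arm is foreseeable, but not certain at every cut-off.

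**BCDVA hides nothing.** If no arm has an event, no effect is lost and the percentages already tell the story. This also stands; for that endpoint the gap is only that a required OR cannot exist. It assumes that gain is analysed separately from loss. SAP 4.2.2 joins the two in one endpoint, and the ceiling argument fails for a composite.

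**Nothing formal depends on it.** Secondary p-values are descriptive, percentages by arm are still shown, and pupil diameter is also analysed by ANCOVA. This is correct, and it is why the point is minor.

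**A stronger reading.** A reader might infer that the primary endpoint could be missed on a strong result. The documents do not support this. It would need both a Wald test in the redacted 9.1.1 code and a Placebo-alone arm with no 15-letter responders, and the assumed placebo rate is not visible. Nor do they support a count of affected ORs, because the handling of gain and loss and the populations per table depend on the redacted list.

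**Conclusion.** The gap is real and minor. SAP 9.1.2 promises outputs that an ordinary fit cannot deliver when a compared arm is empty or full. From the protocol's own pupil means, an empty Placebo-alone arm is foreseeable at the mesopic cut-offs: 97% to 49% for <2.0 mm and 85% to 21% for <2.4 mm at 4.52 mm. Small iris strata are also exposed. For a separate BCDVA gain of at least 15 letters, no events at all is the expected result.

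The probabilities rest on an assumed SD, a normal shape and assumed event rates. The case of only responders follows the same logic but was not quantified. Photopic pupil cut-offs were not assessed, because Table 1 is mesopic. The effect is on descriptive secondary outputs, not on the primary conclusion.

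**What to change.** Before unmasking, add to SAP 9.1.2, unless the redacted code already covers it:

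- If one compared arm has no responders or only responders, fit the same model by Firth penalised likelihood, with a profile-likelihood CI and a penalised likelihood-ratio p-value. Show the counts, with Fisher's exact test as a check.
- If both compared arms have no responders, or both have only responders, report counts and percentages and no OR.

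The same fallback can be named in 9.1.1 for completeness.

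The cost is two or three sentences and one model option, with no extra data. Where the fallback applies, the OR is shrunk slightly and the test is somewhat conservative. An exact treatment-only calculation at 38 per arm, using Wald unless an arm is empty or full and Firth otherwise, gives type I error of 3.5%, 2.9% and 3.9% at common rates of 5%, 10% and 20%. Nothing changes where neither compared arm is empty or full.
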